## 7.9 Twelve-month Follow-up (Clinic Visit)

All subjects who received a CLAAS implant will return to the clinic at 12 months ( $\pm$  30 days) post-procedure for additional follow-up, to include the following assessments:

- Physical examination
- Stroke assessment, to include:
  - Questionnaire for Verifying Stroke Free Status (QVSFS)

- NIH Stroke Scale (NIHSS); the NIHSS must be performed by a neurologist or NIHSS-certified research staff
- Patients in whom a neurologic event is suspected on the basis of the QVSFS, NIHSS, or other signs or symptoms will require a neurologic examination and evaluation performed by a neurologist or clinical designee (e.g., neurology fellow). In patients with confirmed stroke, NIHSS and mRS must be documented, and repeated  $90 \pm 14$  days post-event.
- A transesophageal echocardiogram (TEE) or Cardiac CT Scan\*
- Current concomitant medications documentation. If DAPT has been interrupted or terminated the stop date (and resumption date, if applicable) and the reason for interruption/termination should be recorded. If monotherapy has been initiated due to high bleeding risk, the factors contributing to the high bleeding risk assessment should be documented.
- Documentation of any adverse events occurring since the previous evaluation.

\*NOTE: Subjects evaluated by Cardiac CT which on review are found to have complete seal without thrombus will be considered as having closure success. If review indicates incomplete seal or thrombus, further evaluation by TEE will be required.

## 8.0 Adverse Events and Serious Adverse Events

In this study, patients should be encouraged to report adverse events (AEs) spontaneously or in response to general, non-directed questioning. Any time during the study, the patient may volunteer information that resembles an adverse event (AE). If it is determined that an AE has occurred, the investigator should obtain all the information required to complete the AE CRFs.

### 8.1 Adverse Events (AE)

An adverse event is any untoward medical occurrence, unintended disease or injury or any untoward clinical signs (including an abnormal laboratory finding) in a study subject, whether or not related to the study device.

#### NOTES:

- The definition of AE includes events related to the study device or to the procedures involved but does not imply that there is a relationship between the adverse event and the study device.
- Pre-existing medical conditions or a repeat of symptoms reported prior to the procedure will **not** be reported as an AE. Pre-existing conditions that worsen during a study are to be considered adverse events.
- Planned procedures (scheduled prior to the index procedure) that occur after the index procedure are not considered reportable AEs. Complications from such procedures, however, must be reported.
- Abnormal non-cardiac laboratory findings are not considered a reportable AE unless:
  - The investigator determined that the finding is clinically significant; OR

- o The abnormal laboratory finding required intervention; OR
- o The abnormal laboratory finding required termination of the subject's participation in the study.

## 8.2 Serious Adverse Events (SAE)

A serious adverse event is an adverse event that:

1. Led to a death
2. Led to a serious deterioration in the health of the subject that:
  - a. Resulted in a life-threatening illness or injury
  - b. Resulted in a permanent impairment of a body structure or a body function
  - c. Required in-patient hospitalization or prolongation of existing hospitalization
  - d. Resulted in medical or surgical intervention to prevent life-threatening illness or injury or permanent impairment to body structure or a body function.
3. Led to fetal distress, fetal death or a congenital abnormality or birth defect.

## 8.3 Adverse Device Effect (ADE)

An adverse device effect is an adverse event related to the use of a medical device. This includes:

- Any adverse event resulting from insufficiencies or inadequacies in the Instructions for Use, the deployment, the implantation, the installation, the operation, or any malfunction of the medical device
- Any event that is a result of a use error or intentional misuse

## 8.4 Serious Adverse Device Effect (SADE)

A serious adverse device effect is an adverse device effect that has resulted in any of the consequences characteristic of a serious adverse event.

## 8.5 Unanticipated Adverse Device Effect (UADE)

An unanticipated adverse device effect is any serious adverse effect on the health or safety or any life-threatening problem or death caused by, or associated with, a device, if that effect, problem, or death was not previously identified in nature, severity or degree of incidence in the investigational plan or application (including a supplementary plan or application), or any other unanticipated serious problem associated with a device that relates to the rights, safety or welfare of subjects.

NOTE: An anticipated serious adverse device effect (ASADE) is a serious adverse device effect which by its nature, incidence, severity, or outcome has been identified in the investigational plan.

## 8.6 Device Deficiencies, Malfunctions, and Use Error

Investigators are instructed to report all possible device deficiencies, malfunctions, misuse or use error observed during the course of the trial. These incidents will be documented in the case report form provided as follows:

- **Device deficiency:** Inadequacy of a medical device related to its identity, quality, durability, reliability, safety or performance. NOTE: Device deficiencies include malfunction, use error, and inadequate labeling. They may or may not affect device performance or lead to an adverse event.
  - **Device malfunction:** Failure of an investigational medical device to perform in accordance with its intended purpose when used in accordance with the Instructions for Use or protocol. NOTE: A device malfunction occurs when the device is used in compliance with the Instructions for Use but does not perform as described in the Instructions for Use.
  - **Use error:** Act or omission of an act that results in a different medical device response than intended by the manufacturer or expected by the user. NOTE 1: Use error includes slips, lapses and mistakes. NOTE 2: An unexpected physiological response of the patient does not itself constitute a use error.
    - **Device misuse:** Any use of the investigational device by an investigator that is contradictory to the application described in the Instructions for Use will be categorized as device misuse. This is a form of Use Error.

## 8.7 Documentation

Adverse events must be listed on the appropriate CRF. All AEs will be characterized by the following criteria which are detailed in the definition section:

- Intensity or Severity
- Relatedness
- Outcome
- Treatment or Action Taken

## 8.8 Reporting

### 8.8.1 General Adverse Event Reporting Procedures

Investigators are required to keep records on "all relevant observations, including records concerning adverse device effects (whether anticipated or unanticipated)" according to 21 CFR 812.140. Adverse event collection will occur from the point of study enrollment to study closure. All new or worsening (from baseline) cardiovascular adverse events will be captured on the AE CRF through the 5-year follow-up telephone contact. Independent monitoring will be conducted (§12.1) to review source documentation and verify the complete and accurate capturing of adverse events.

The general procedure for investigators reporting any adverse event is as follows:

- If an adverse event occurs, complete all sections of the Adverse Event CRF. Note:
  - Documented pre-existing conditions are not considered to be reportable AEs unless there is a change in the nature or severity of the condition
  - Planned procedures (scheduled prior to the index procedure) that occur after the index procedure are not considered reportable AEs. Complications from such procedures, however, must be reported.
  - Abnormal non-cardiac laboratory findings are not considered a reportable AE unless:

- The investigator determined that the finding is clinically significant; OR
- The abnormal laboratory finding required intervention; OR
- The abnormal laboratory finding required termination of the subject's participation in the study.

- Each unique event/diagnosis must be documented separately
- The AE CRF must be reviewed by the investigator

For adverse events not meeting the criteria for an SAE or (potential) UADE, the Sponsor recommends that the Investigator notify the Sponsor within 10 working days of first learning of the AE using the electronic data capture (EDC) CRF. If necessary, the Investigator may be requested to provide de-identified copies of source documentation (e.g., physician/nurse notes or summaries) regarding the event.

The Investigator must also notify the responsible EC regarding new and significant safety information and any events identified by Conformal Medical that require expedited FDA or other regulatory authority reporting as serious, unexpected, and related to the investigational device. It is the responsibility of the investigator to ensure site-specific IRB/EC reporting requirement are met.

The Sponsor is responsible for reporting SAEs and device deficiencies to regulatory authorities in line with applicable regulatory requirements and for reviewing the risk analysis, determining the need for corrective or preventative action, and informing investigators and regulatory authorities accordingly.

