#### 5.3.3.1 Secondary Safety Endpoints

5.3.3.1.1 **Major procedure-related complications**, defined as the composite of cardiac perforation, pericardial effusion with tamponade, ischemic stroke, device embolization, and major vascular complications as related to the study device or procedure [evaluated in-hospital]

5.3.3.1.2 **Major safety events**, defined as the composite of all-cause mortality, overt CNS injury (Neuro ARC defined), and major bleeding (BARC Type 3-5)

5.3.3.1.3 **Mortality**, classified as cardiovascular or non-cardiovascular reported cumulatively and individually

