6.2.2.2.7 Moderate or severe mitral valve stenosis (mitral valve area <1.5 cm^2)

6.2.2.2.8 Complex atheroma with mobile plaque of the aorta

6.2.2.2.9 Patient has evidence of cardiac tumor

### 6.3 Subject Screening

The study site will maintain a log of all screened and consented subjects. Reasons for meeting study criteria but failing to be enrolled will be captured on the screening log and entered into the database.

Potentially eligible subjects will undergo the process of informed consent (§6.4) prior to the performance of any study-specific assessments.

Potentially eligible subjects will be enrolled in the study only when the CLAAS Access Sheath has been introduced into the patient's body. Patients who do not meet general or echocardiographic eligibility criteria, or in whom the CLAAS Access Sheath is not introduced, will not be enrolled in the study.

Screen failures may be re-enrolled at a future date if it is determined that the eligibility criteria that initially excluded them from participation are no longer applicable (e.g., a thrombus identified on the initial TEE has resolved, a prior stroke is now outside of the exclusion window) or larger device is available.

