## **6.5 Subject Enrollment**

Potentially eligible subjects who meet all general inclusion criteria, and no general exclusion criteria and who have consented to participate in the trial will undergo the protocol-specified screening assessments to confirm eligibility. At the time of the index procedure, Echo will be evaluated to confirm that adequate echocardiographic images can be acquired and that no echocardiographic exclusion criteria (§6.2.2.2) are met.

Subjects meeting all inclusion and no exclusion criteria, and in whom the CLAAS Access Sheath is introduced into the patient's body, will be enrolled in the trial. Subjects who meet all eligibility criteria, but in whom the CLAAS Access Sheath is not introduced, are classified as screen failures, which must be documented in accordance with §6.3.

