	
survival status, QVSFS, concomitant medication documentation, and reporting of any adverse events that may have occurred since the pre-discharge assessment.
 
The Questionnaire for Verifying Stroke-Free Status (QVSFS) and NIHSS must be completed at baseline and during each clinic visit to screen for interceding signs and symptoms of stroke or TIA. The modified Rankin Scale (mRS) must also be completed at baseline to establish the pre-stroke baseline value. For telephone contacts, stroke screening will consist of the QVSFS only. If a neurologic event is suspected at any time point, a formal neurologic examination and evaluation (to include the mRS) must be performed by a neurologist.
 
 Female subjects of childbearing potential must have a pregnancy test (by site standard method) within 7 days prior to the index procedure to confirm study eligibility criteria.
 
 Laboratory testing should be performed per site standard practice and should include CBC and serum creatinine.
 
 A 12-lead ECG should be performed at baseline and repeated with any signs or symptoms of myocardial ischemia.
 
 Patients with a history of stroke are required to have a baseline MRI (or CT, if MRI is contraindicated) performed within 90 days prior to the scheduled index procedure. Brain imaging need not be repeated if an MRI or CT performed within 90 days pre-procedure as part of the standard of care is available. Patients with history of significant brain trauma or intra-cranial surgery should have a post procedure/event CT or MRI available for review.
 
 An initial evaluation of echocardiographic eligibility based on review of the pre-procedure TTE and/or TEE (or cardiac CT, if that modality is the site standard of care for pre-procedure anatomic assessment) should be performed prior to the index procedure.
 
 TEE (or CT) performed within 90 days prior to consent will be accepted, otherwise TEE must be conducted after consent.
 
TTE performed within 6 months prior to consent will be accepted, otherwise TTE must be conducted after consent.
 
TEE performed after implant delivered, prior to tether release.
 
At time of index procedure, ICE performed to confirm eligibility criteria prior to enrollment.

--	---

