### 7.3.3 Transseptal Puncture

Percutaneous femoral vein access and transseptal puncture should be performed per physician standard practice using a standard commercially-available transseptal access system.

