### 7.3.6 CLAAS Implant Deployment

After eligibility has been confirmed and the CLAAS Access Sheath has been introduced into the patient's body, the patient is enrolled in the study and should undergo implantation of the CLAAS Implant per the device Instructions for Use.

Procedural details should be entered into the eCRF. ACT should be measured at the onset of the procedure and at regular intervals throughout the procedure per routine hospital practice.

The procedure is considered complete once the last venous access sheath is removed or the patient has been discharged from the cath lab, whichever is first.

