#### **10.3.4 Additional Analyses**

The following data will be summarized using descriptive statistics presented by treatment group in the ITT and IP populations:

- Frequency (number and percentage of patients) with each type of concomitant medication
- Frequency (number and percentage of patients) with each site-reported Treatment Emergent AE overall and by MedDRA system organ class and preferred term (a treatment emergent AE is an AE that started or worsened during or after the index procedure)
- Frequency (number and percent of patients) with each site-reported Treatment Emergent Serious AE overall and by MedDRA system organ class and preferred term
- Protocol deviations (number and percentage of patients with each deviation type)
- Detailed listings on primary and secondary endpoints, site-reported AEs, and protocol deviations

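### Adverse event collection starts at Access Sheath introduction (8.8.1), later than the index-procedure start used by the treatment-emergent analysis (10.3.4, Version B)

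*Combined protocol and SAP*

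**What the plan says.** All references are to Version B of the combined protocol and SAP.

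- **Collection window.** Section 8.8.1: "Adverse event collection will occur from the point of study enrollment to study closure".
- **Enrollment.** Section 6.3 says potentially eligible subjects "will be enrolled in the study only when the CLAAS Access Sheath has been introduced". Section 7.3.6 gives the order: "After eligibility has been confirmed and the CLAAS Access Sheath has been introduced into the patient's body, the patient is enrolled in the study". The ITT definition in 10.2.1 uses the same point.
- **What comes before enrollment.** Table 3, footnote 12: "At time of index procedure, ICE performed to confirm eligibility criteria prior to enrollment". Section 7.3.3: "Percutaneous femoral vein access and transseptal puncture should be performed per physician standard practice using a standard commercially-available transseptal access system".
- **Schedule.** The adverse events row of Table 3 is marked in the Index Procedure column.
- **Analysis window.** Section 10.3.4: "a treatment emergent AE is an AE that started or worsened during or after the index procedure". Its tables and listings are for the ITT and IP populations.
- **Patients stopped early.** Under 6.5, otherwise eligible subjects "in whom the CLAAS Access Sheath is not introduced, are classified as screen failures". Under 6.3, patients who fail the echocardiographic criteria are not enrolled either.

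**The concern.** The safety tables can hold only what the site was told to record. Section 10.3.4 wants everything that begins during the index procedure, while the opening rule of 8.8.1 tells the site to start part-way through it. The excluded interval contains an intracardiac imaging study and, very likely, venous access and transseptal puncture. Section 8.9 lists recognized risks that could arise there, such as anesthesia effects, contrast reactions and access-site complications.

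Two things are at stake. For a patient who goes on to be enrolled, an early event may be missing from a table that should include it. For a patient whose procedure is abandoned before the sheath, for example because the eligibility ICE shows thrombus, an invasive exposure has taken place and the plan has nowhere to report its harms. This is a small descriptive study whose purpose includes gathering preliminary safety data for a pivotal trial (4.3), so complete procedural safety data matter more than usual.

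**Working it through.** The plan states no figure on this point, so the check compares the texts.

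1. **Locate the start of collection.** By 8.8.1 it is enrollment. By 6.3, 7.3.6 and 10.2.1, enrollment is Access Sheath introduction. Appendix A words the ITT enrollment point as introduction of the delivery system, which also follows the eligibility ICE.
2. **Locate the index procedure relative to that point.** Footnote 12 is explicit: the eligibility ICE belongs to the index procedure and precedes enrollment. For the puncture the order is inferred. It uses a separate commercial system and is described in 7.3.3, ahead of eligibility confirmation (7.3.4) and deployment (7.3.6). Section 7.3.6 says when the procedure ends; no section says when it begins.
3. **Compare the windows.** The 10.3.4 rule opens with the index procedure. The first sentence of 8.8.1 opens later, inside it. The ICE alone establishes the difference; the puncture order is not needed.
4. **Ask what else captures an event in the interval.**

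| Event before the sheath | Within the 8.8.1 enrollment window? | Other route | Result |
|---|---|---|---|
| Serious; patient later enrolled | No | 8.8.2 asks for notice of any SAE within 2 working days by eCRF, with no enrollment limit | Covered |
| Non-serious cardiovascular; patient later enrolled | No | The next sentence of 8.8.1 captures cardiovascular events that are new or worse than baseline | Arguably covered |
| Non-serious, non-cardiovascular; patient later enrolled | No | Only the Index Procedure mark in Table 3 | Clear conflict |
| Any event; procedure stops before the sheath | No | 8.8.2 if serious; the 6.3 screening log records why an eligible patient was not enrolled | Outside ITT and IP; in no 10.3 table or listing |

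5. **Scale.** At the target of 20 subjects (10.1), one subject is 1/20 = 5 percentage points in any adverse event row. That describes how coarse the tables are. It does not measure how often an event would be lost, and the documents give nothing from which to estimate that.

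**The case against.** The best reply is that the important events are already caught. Perforation, tamponade and major access injury are cardiovascular and new from baseline, so the second sentence of 8.8.1 can be read to require them on the AE form. They would normally be serious, so 8.8.2 applies. Section 12.2 requires an index-procedure report with complications in each enrolled patient's file, and 8.8.1 has monitors check adverse event capture against source. The composite of major procedure-related complications, "defined as the composite of cardiac perforation, pericardial effusion with tamponade, ischemic stroke, device embolization, and major vascular complications", is evaluated in-hospital in its own right, with ITT as the primary population. This largely stands. A reader might infer that the secondary safety endpoint would lose perforations or tamponades in enrolled subjects; the documents do not support that.

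It can also be said that 10.3.4 is an analysis rule and sets no collection start. That is correct, but an analysis rule that reaches further back than collection still cannot be fully met. The Index Procedure mark in Table 3 gives no clock time, yet the same column holds the pre-enrollment ICE, so its natural reading includes that step. The Screening mark in the adverse events row should not be relied on, because the only note attached to it is about TTE timing.

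Finally, starting collection at enrollment is a legitimate design choice, and 8.1 defines an adverse event in a study subject. That would be a full answer if enrollment coincided with the start of the procedure or if 10.3.4 used the same start. Neither is so.

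**Conclusion.** The inconsistency is real and minor. The enrollment-based window in 8.8.1 opens later than the one 10.3.4 analyzes, and an invasive step lies between them. The clear gap is mainly non-serious or non-cardiovascular events before the sheath, plus events in patients whose procedure ends before it. The primary performance endpoint is not touched.

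The conclusion rests on footnote 12 for the order of ICE and enrollment, which is explicit. That the puncture also precedes the sheath is probable but inferred, and the finding holds without it. For new cardiovascular events, coverage depends on whether the second sentence of 8.8.1 is read as independent of the enrollment start or as nested within it; the text allows both readings, which is itself a reason to clarify it.

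A reader might want to put a probability on a missed event. That would need a rate of pre-sheath events and a chance that the site ignores Table 3 and the other routes, and the documents supply neither. Events between consent and the index procedure are not part of this point: 10.3.4 does not count an event as treatment-emergent unless it starts or worsens during or after the procedure.

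**What to change.** Reword the opening rule of 8.8.1 so that adverse events are collected from the start of the index procedure, defined as first venous access or procedural imaging, whichever is first, through study closure. This also supplies the missing definition of when the procedure starts, which 10.3.4 needs.

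Add to 10.3.4 a separate listing of any adverse event in consented patients who began the index procedure but were not enrolled, kept outside the ITT and IP tables. The enrollment point, the two analysis populations and the treatment-emergent definition stay as they are.

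The cost is one changed sentence, one short listing, and AE forms for the few patients stopped before the sheath. No visit, test or subject is added.
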